# 1 Synopsis

Protocol title	Multimodal monitoring of radiotherapy response in squamous cell cancer (SCC) in head & neck, lung, oesophagus, anal canal and uterine cervix – a basis for personalised radiotherapy
Development phase	Observational study
Study population	Patients with previously untreated SCCs aimed for radiotherapy with curative intent of the oral cavity, oropharynx, uterine cervix, oesophagus, anal canal or lung.
Endpoints	
Primary end-point
 
Loco-regional control 2 years after completion of radiotherapy
 
Secondary end points
 

1. Loco-regional tumour control (or response) 8 (-2 - +4) weeks after completion of radiotherapy

2. Patterns of failure

3. Progression free survival at 2 years

4. Overall survival at 2 and 5 years

5. Changes in imaging and metabolic data

6. Site specific toxicity at 12 months after completion of radiotherapy

Study design	Non-randomised, prospective, multi centre, observational study. Patients with previously untreated SCCs aimed for radiotherapy with curative intent of the oral cavity, oropharynx, uterine cervix, oesophagus, anal canal or lung are recruited. Multimodal, functional imaging data are collected before and during the early phase of radiotherapy. In parallel to the imaging data, tumour biopsies and blood will be collected for molecular analyses that may provide explanatory information to the imaging information.
Overall aim	Prediction of short and long term outcome of treatment for squamous cell cancer (SCC) by monitoring tumour response during early treatment phases.

**Specific aims**

Correlate changes in imaging bio-markers to corresponding changes in tissue or blood bio-markers by repeated imaging and biopsies for better understanding of the image parameters.  
To correlate data from multiparametric imaging to specific outcome  
Validation of early bio-imaging predictors of tumour response and patient outcome.

**Eligibility criteria****Inclusion criteria**

1. Morphologically (pathology or cytology) verified, previously untreated SCCs of the oral cavity, oropharynx, uterine cervix, oesophagus or lung.
2. The patient should be planned for treatment with radiotherapy alone or in combination with concomitant medical therapy
3. The tumour shall be radiologically and/or visually identifiable and accessible for biopsy without the need for general anaesthesia or other major interventions
4. The patient must be at least 18 years of age, able to understand the given information and, leave a written informed consent to participate

**Exclusion criteria**

1. The patient is unwilling to participate in the study
2. Patients with adjuvant post-operative radiotherapy (i.e. no visible remaining tumour)
3. Pregnancy or lactation
4. Contraindications to investigations with MRI, gadolinium contrast or PET-tracers
5. Patients with an estimated GFR <60 ml/min/1.73m^2.
6. Severe co-morbidities that are judged to significantly compromise survival in a two-years perspective.

**Duration of study**

The first acquisition of image data and tissue samples is performed as close as possible to start of radiotherapy. The time for the second acquisition of image data and tumour tissue will be after 1-2 weeks of treatment. The precise timing will be optimised after the separate analysis of the 20-30 first patients. The patients will then

be followed according to clinical routines for at least two years for evaluation of tumour control. In patients with remaining tumour or recurrent disease the site of the tumour will be recorded and compared with the position of the original site. Survival of patients will be followed for five years by the Swedish population registry.

**Radiotherapy and possible neo-adjuvant, concomitant or adjuvant therapy**

The standard treatment schedules according to clinical routines and decisions will be followed irrespective if the patient is taking part in the study or not. Specific information on all anticancer therapy (doses and timing) will be recorded for each patient. The observation will commence at start of radiotherapy irrespective when and how other supporting therapies are used.

**Efficacy evaluation**

1. Loco-regional tumour control (or response) 8 (-2 - +4) weeks after completion of radiotherapy
2. Patterns of failure
3. Progression free survival at 2 years
4. Overall survival at 2 and 5 years
5. Changes in imaging and metabolic data
6. Site specific toxicity at 12 months after completion of radiotherapy

**Pilot study**

The first 30 patients will have the study procedures at different time points after start of radiotherapy. Different sequencing of biopsy and imaging procedures will be employed. This is in order to find the shortest interval between start of therapy and imaging to be able to detect differences in functional imaging parameters. The results will be used for establishing the precise schedule for remaining patients. These patients will not be included in the final analyses.

**Interim analysis**

After inclusion of 100 patients for at least two months an interim analysis will be performed. The reason is to identify parameters that exhibit a rapid change between the two assessment times, in a proportion of patients. Those parameters that do not exhibit such changes will be excluded from further assessments. The protocol will subsequently be refined.

**Statistical methods**

To find potentially relevant patterns of response in the large amount of data for each patient, chemometric methods will be applied

To estimate the degree of agreement between predicted and observed response the Cohen's Kappa will be used.

Criteria for evaluation	Patients who have undergone per protocol imaging sessions before and during therapy
Planned sample size	412 patients
Analysis plan	The primary endpoint will be analysed when median follow up is two years.
Duration of the study	Three to four years inclusion, five year follow-up after inclusion of the last patient.

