## **4.2 End points**

### **4.2.1 Primary end point**

- Loco-regional control 2 years after completion of radiotherapy

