## 9.6 End of treatment or follow-up

Follow-up by the protocol ends when any of the events below occurs:

- If 5 years of follow-up is reached
- If residual tumour or a locoregional recurrence is diagnosed that cannot be treated with curative intent. Survival will then be followed by the Swedish population registry
- In cases of other serious medical conditions, follow-up ends as judged by the investigator. Survival will then be followed by the Swedish population registry
- If the patient dies before 5 years' follow up
- Withdrawal of consent

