### **12.4 Pilot study**

The first 20-30 patients will be part of a pre-study where the timing and protocols for investigation are optimised. These patients will not be included in the analysis of the main study. One of four patients will be randomly chosen for belonging to the “hypothesis generation group” (HGG). Their data will be analysed in the search of a number of predictive parameters for outcome. The remaining patients’ data will be used for validation of hypotheses. The HGG will not be used in this validation process. The first analyses will be performed when the number of study patients is reached. The second analysis will be performed two years after including the last patient. The third analysis will be performed when five years have passed since the last inclusion of a patient.

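### The synopsis ties the primary analysis to a two-year median follow-up, which does not fit the two-year endpoint, and section 12.4 sets three other dates without naming one as primary

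*Protocol*

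**What the plan says.** The primary endpoint (Protocol, section 4.2.1) is "Loco-regional control 2 years after completion of radiotherapy".

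The timing of its analysis appears in one place only, the Analysis plan row of the synopsis: "The primary endpoint will be analysed when median follow up is two years".

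Section 12.4 gives a different schedule of three looks. One comes at the end of accrual: "The first analyses will be performed when the number of study patients is reached". Another is counted from the final inclusion and is the one closest to the endpoint's horizon: "The second analysis will be performed two years after including the last patient". The remaining look, at five years after the final inclusion, matches the longest survival endpoint. The section links none of the three to the primary endpoint and does not refer to median follow-up.

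Three other statements bear on the point. Under Duration of study, the synopsis says patients will "be followed according to clinical routines for at least two years for evaluation of tumour control". On the clock, it says "The observation will commence at start of radiotherapy irrespective when and how other supporting therapies are used", but does not connect this to the median. Section 9.6 ends protocol follow-up at death and, among other events, "If residual tumour or a locoregional recurrence is diagnosed that cannot be treated with curative intent".

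**The concern.** The endpoint is a status at a fixed time after radiotherapy. A patient contributes a complete observation only after loss of control or after two years from the end of treatment. When the median of potential follow-up is two years, about half the patients are by construction short of two years, whatever the accrual pattern. The synopsis rule therefore calls for the primary result while much of the endpoint is still unobserved.

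The second problem is that the two schedules are not joined. A reader of section 12.4 would probably take the second analysis as the primary one, whereas a reader of the synopsis would analyse well before it. If neither is named in advance, the choice of which look counts can be made after data have accrued. That sits badly with a study whose stated purpose is validation.

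**Working it through.** The protocol gives no maturity figure to reproduce, so the check works out how mature the data are at each date.

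**Inputs**
- Accrual *A* = 3 to 4 years (section 5.1); uniform accrual is assumed.
- Lag *L* from inclusion to end of radiotherapy = 7 to 9 weeks (0.134 to 0.172 years), assumed. It is built from 7 weeks of treatment (section 3.1 mentions 6-7 weeks, for head and neck only) plus up to two weeks of lead-in (section 7).
- *c* = time from inclusion to the start of the follow-up clock: 0 if the clock starts at inclusion, *L* if it starts at the end of radiotherapy.
- *S* = control at two years, 0.5 to 0.8 (assumed), with constant hazard *h* = −ln(*S*)/2.

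**1. Date of the trigger, potential follow-up.** At calendar time *T* the median is *T* − *A*/2 − *c*. It reaches 2 at *T* = 2 + *A*/2 + *c*, which is 2 − *A*/2 + *c* years after the last inclusion.
- *A* = 4, *c* = 0: 0 months.
- *A* = 3, *c* = 0: 6 months.
- *A* = 3, *c* = 9 weeks: 0.5 + 0.172 = 0.672 years, or 8.1 months.

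**2. Share with the full window at that date.** (*T* − 2 − *L*)/*A* = 0.5 − (*L* − *c*)/*A*. The lowest value is 0.5 − 0.172/3 = 0.44; the highest is 0.50, when *c* = *L*.

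**3. Share with unknown status.** These patients are under two years from radiotherapy and have not failed. The share is (1/*A*) × ∫ e^(−*hs*) d*s* from *s* = 2 − *A*/2 − (*L* − *c*) to 2, with anyone not yet past radiotherapy counted as unknown.
- *S* = 0.8 (*h* = 0.1116): highest (0.172 + 0.2/0.1116)/4 = 0.49; lowest (0.9457 − 0.8)/(3 × 0.1116) = 0.44.
- *S* = 0.5 (*h* = 0.3466): highest (0.172 + 0.5/0.3466)/4 = 0.40; lowest (0.8409 − 0.5)/(3 × 0.3466) = 0.33.

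**4. Section 12.4 dates, share with the full window.**
- First (full accrual): (*A* − 2 − *L*)/*A* = 28-29% for three years of accrual, 46-47% for four.
- Second: (*A* − *L*)/*A* = 1 − 0.172/3 = 94% to 1 − 0.134/4 = 97%.
- Third: 100%.

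**5. Cost if the endpoint is scored by kappa.** The protocol names kappa for predicted against observed response but no statistic for the primary endpoint, so this link is an inference. Alpha is not stated either; one-sided 5% is assumed. With κ0 = 0.4, κ1 = 0.7 and a 50/50 split, the large-sample variance is (1 − κ²)/*n*, and power = Φ[(0.3√*n* − 1.645√0.84)/√0.51]. For 90% power this needs 66 patients, against 63 in section 12.1. At 20% responders the same approach needs 101 against 80, so it is not the protocol's exact method.
- *n* = 70, mature data: 92%.
- All known statuses at 50% control: 70 × (1 − 0.40) to 70 × (1 − 0.33) = 42 to 47 patients, power 73-78%. The patients added here are all failures, so the split would tilt away from 50/50 and power would be a little lower.
- Complete windows only: 70 × 0.44 to 70 × 0.50 = 31 to 35 patients, power 59-65%.

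**6. Cost for the control rate itself.** A simple proportion among known statuses is biased, because failures become known early. At a true 80% it reads 0.4425 × 0.8/(1 − 0.4903) = 69% to 0.5 × 0.8/(1 − 0.448) = 72%. A Kaplan-Meier estimate is unbiased. In simulation with *n* = 70, its standard error rises from 4.8 to 5.5-5.9 percentage points at 80% control, and from 6.0 to 7.0-7.5 at 50%.

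**The case against.** **Definitions can wait for the SAP.** The clock origin, and whether follow-up is potential or observed, are commonly left to an analysis plan, which is not at hand. This stands, and their absence alone is not counted as a fault. It does not settle the point, since the protocol itself fixes a trigger in one place and another schedule in a second, and any analysis plan would inherit both.

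**The schedules may be compatible.** The three dates in section 12.4 line up naturally with the 8-week, 2-year and 5-year endpoints, and the protocol does not state two rival primary dates. The plan to follow each patient for at least two years is not an analysis date. All this is fair, but the link is never written down, and the only sentence that mentions the primary endpoint uses the median.

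**Little harm follows.** A nearly mature analysis is already scheduled, section 12.2 foresees re-analysis with longer follow-up, and section 15.5 says results do not affect care. This stands and limits the severity.

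**Two stronger readings are tempting, and the protocol supports neither.**
- A reader might infer that the trigger could fall as late as 26 months after the last inclusion, or never. If every failure ended follow-up, a median of observed follow-up would indeed put it at 21-26 months at 50% control and never at 40%. Section 9.6, however, ends follow-up only for failures that cannot be treated with curative intent. If half are salvageable (assumed), the dates become about 7-14 and 10-16 months. Section 9.6 also lists death, which these figures leave out. No single range can be claimed.
- A reader might quote 59-65% as the power of the primary analysis. That needs kappa to score the primary endpoint and known early failures to be discarded; the protocol states neither. The wording about response and responders in section 12.1 and the synopsis may refer to the 8-week endpoint, in which case this loss does not arise.

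**Conclusion.** The point holds as an unreconciled schedule with a trigger unsuited to the endpoint. On the potential-follow-up reading, the synopsis would bring the primary analysis forward to a date when about half the windows are complete. That figure of about half does not depend on the accrual pattern. The exact dates and the unknown shares rest on uniform accrual, a 7-9 week lag and a constant hazard. On the observed-follow-up reading the direction is clear (later, more mature) but the amount is not.

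The consequence depends on the estimator. A censored estimate loses only precision, a simple proportion understates control, and kappa, if it is used for this endpoint, loses power. The damage arises only if the synopsis sentence is followed. The point should be fixed, but it does not undermine the study.

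**What to change.** Delete the median trigger from the synopsis, and have the synopsis and section 12.4 name the same single primary-analysis date. The least change is to designate the existing second analysis, two years after the last inclusion. Preferably it would be set when the last included patient has reached, or would have reached, two years after completion of radiotherapy. That is 7-9 weeks (about two months) later and completes the remaining 3-6% of windows; this last step is a refinement rather than a necessity.

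The edit is one sentence in each of two places. The cost is time. Against the potential-follow-up reading of the synopsis, the primary result comes later by 24 months + *L* − (months from last inclusion to trigger). The extremes are 24 + *L* − (6 + *L*) = 18 months and 24 + 2.1 − 0 = 26 months. Keeping the second analysis at its present date gives 24 − 8.1 = 16 to 24 months. The delay is shorter if the median was meant as observed follow-up. Either date lies within the five years of follow-up already planned and needs no extra visits.

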## 3 Background and introduction

### 3.1 Background

The knowledge of factors determining treatment effect in cancer therapy is important in the treatment selection for individual patients. In some cancers impressive progress has been made over the years and has resulted in major improvements in disease control, e.g. in breast cancer. The basis for treatment selection is usually the assessment of pre-treatment characteristics of the patient and the individual tumour. Expression of certain genes, hormonal status and proliferation parameters are some examples of individual tumour properties in clinical routine use. The development in the field of molecular biology during recent decades is not reflected in a similar improvement of therapeutic results for most cancers. Particularly this is the case with most SCCs. In Sweden about 2000 SCC are diagnosed every year within lungs, head & neck, anus, cervix and esophagus.

For a large proportion of cancers the knowledge of pre-treatment parameters of predictive capacity is sparse. A number of biomarkers or combinations thereof have been identified (e.g. HPV, EGFR, ...). In the majority of cases they correlate to outcome of treatment and can therefore be described as prognostic and not specific enough for personalised therapy. In the absence of strong predictors an alternative is to explore the early changes after initiating therapy. Such changes have the potential to be relevant in the assessment of individual tumour response. It is assumed that the changes will also give leads to factors present already before treatment, which are not yet identified.

Cancer treatments; radiotherapy, chemotherapy and/or targeted therapies are frequently administered during an extended time period. The evaluation of effectiveness usually takes place a couple of months after end of therapy. Early response is commonly evaluated by agreed "*Response Evaluation Criteria in Solid Tumors*" (RECIST). Basically, measuring the diameters of tumour contours on radiological examinations makes the assessment. The results given by such end-points will not be able to discriminate between different patterns of response as for example, differential responses in subsets of the tumour. Furthermore, the time between start of therapy and evaluation often comprises the therapeutic interval in which there still exists a possibility to adapt or completely change a suboptimal treatment. Structural changes in tumours are slow compared with changes in biochemistry and other functions.

Detection of early response predictors will therefore be an important adjunct to further development of cancer therapy. Since many years, in radiotherapy, there are examples of early changes that are predictive for outcome. E.g. changes in metabolism measured by FDG-PET and labelling index by infusion of halogenated pyrimidines in vivo have both shown a strong predictive capacity as early as one week into a 6-7 weeks treatment for head and neck cancer e.g. (1,2). It is noteworthy that similar results arise from studies of completely different processes. More recent observations in cases such as cervical cancer (3,4) and head and neck cancers (5) support the hypothesis that treatment effects give rise to complex responses in different cellular processes. Such processes may be identified by a number of methods. The combination of different methods is likely to be more effective. Functional imaging techniques, as positron

emission tomography (PET) combined with magnetic resonance imaging (MRI), offer complementary information that may assess a multitude of biomarkers in patients with SCC. Diffusion, perfusion, metabolism, proliferation are examples of properties that may be studied by static and/or dynamic methods. In the present literature usually one or a few imaging biomarkers have been analysed at the time and only in small patient populations, many with encouraging results e.g. (5-9). They have rarely been further validated and thus, not established as a basis for clinical decisions (7,10).

The imaging biomarkers under study correspond to a number of molecular events in the tumour. It is therefore natural to investigate an array of molecular changes in parallel. The parallel investigations may also spread light over the influence of tumour heterogeneity. The infrastructure of the Department of Oncology in Umeå has access to clinical, dedicated MR-PET equipment for research and development. A core facility with metabolomics and molecular pathology is also a part in the project. At the radiotherapy department in Lund there is presently a MR system available and also availability to PET-CT equipment at the hospital for investigation of study patients. Furthermore another PET-CT equipment will be installed at the radiotherapy department in Lund in near future.

The concept of metabolomics is the systematic study of the unique chemical fingerprints caused by specific cellular processes, where the analysis is expanded to hundreds to thousands of metabolites (< 1kDa). This can be compared to traditional metabolic studies where only a limited set of molecules is studied. Metabolomics has attracted large interest in recent years, since it has the power and scope to resolve fundamental biological issues that cannot be readily addressed using other approaches. Metabolomics information represents a more complete description of the organism closest to the function or phenotype, but also more complex than explanations based on, e.g. functional genomics, proteomics and transcriptomics. To model the systems biology from genome to function or phenotype (tumour) based on these pieces of information, using parametric methods is not realistic today. However, to analyse the systems biology by non-parametric methods as applied in metabolomics research is fully feasible. Current studies of metabolomics are, however, limited to samples representing the whole system or by invasive methods obtained samples and cannot detect heterogeneities in tumours or even locate the signalling tissue. In order to move the metabolomics from isolated research studies to diagnostic predictive and monitoring systems, there is a need for more powerful data collection and data processing tools. Both PET and MRI have the capability to measure metabolic activity and system vascularity in volume elements of approximately 1-10 mm^3. The molar sensitivity of a PET system is very high, in the order of 10^-15 molar. The combination of the high spatial resolution of the MRI technique and the high sensitivity of the PET system will enable detection of, e.g. therapy-resistant tumour sub-volumes. Sampling of repeated functional images will be an integrated part of the large-scale data sampling. The initial aim of the project will be to determine metabolic fingerprints over time from samples and images, and correlate these to disease, therapy and outcome. Chemometrics and projection-based methods such as Principal Component Analysis (PCA), Partial Least Squares (PLS) and Orthogonal PLS (OPLS) are well-established methods in metabolomics for predictive modelling, powerful data visualization and model interpretation (Holmes & Antti 2002, Trygg, Holmes et al. 2007). However, time trends of a biological system are

not generally considered in metabolomic studies. In the current projects the time aspect will be implemented as part of a holistic-system biology approach. This approach is, in general, assumed to give more comprehensive information of the metabolic mechanism associated with biological functions and disease (Madsen et al. 2010).

